10.3.2. Dyslipidaemia

AE lipid profile changes, defined in the Dyslipidaemia SMQ, will be reported. See [Appendix B](#) for a list of the preferred terms and their associated codes. These events will be summarized separately by the MedDRA system organ class (SOC), treatment group, and preferred term (PT) as a subset of all TEAEs.

In order to explore the relationship between dyslipidaemia and the investigational product, the following time-to-event analyses will be performed:

- Time to first onset of treatment-emergent dyslipidaemia
 - The time to the start of the first episode will be calculated by date of onset of first episode – date of first dose of investigational product + 1.

The analysis of time to event will include the number of subjects with the event (first onset) and the number of subjects without the event (censored), descriptive statistics of time for those with

an event, and range in days for all subjects. Kaplan-Meier (KM) estimates will be calculated by treatment group. The quartiles, including the median time-to-event and their respective 2-sided 95% CIs, will be presented. KM estimates will be plotted as a “survival curve” for each treatment group, with the number at risk identified. The comparison of OCA to placebo will be summarized using a log-rank test stratified by randomization strata factor.

10.4. Clinical Laboratory Evaluations

Clinical laboratory evaluations during the DB phase are assessed at the central laboratory. A listing of available laboratory reference/normal ranges for each laboratory parameter will be provided including age, sex, values with units. All analyses of lipoprotein will include fasted samples only.

Quantitative hematology, coagulation, serum chemistry, apolipoprotein and nuclear magnetic resonance (NMR) lipoprotein panel laboratory parameters will be summarized by treatment group in SI units using arithmetic summary statistics as described in [Section 6.2.1](#) at Baseline and at each scheduled DB post-Baseline visit. Change from Baseline will also be summarized in the same manner. Re-tests or unscheduled visit results after first dose of investigational product in the DB phase will not be summarized but will be included in the data listings.

In addition, shift tables (ie, low-normal-high at Baseline versus low-normal-high at DB post-Baseline Visit in a 3-by-3 contingency table) from Baseline to worst value, last value, and at each scheduled DB post-Baseline visit will be provided for hematology, coagulation, and serum chemistry by treatment group.

Urinalysis results will not be summarized but will be provided in a data listing.

Listings of all laboratory values will flag values outside of the normal range as high (H) or low (L) and indicate whether or not a value is clinically significant (CS), based on investigator judgment.

For laboratory test results that are below the quantifiable limits:

Imputed laboratory result = (numeric portion of the result) \times 0.9.

For laboratory test results that are above the quantifiable limits:

Imputed laboratory result = (numeric portion of the result) \times 1.1.

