#### **4.5. Summary of Known Potential Risks with Investigational Product**

Investigators are referred to the current IB for a thorough presentation of the safety data associated with OCA. An overview is as follows:

Pruritus is a common symptom of chronic cholestatic diseases such as PBC and PSC. In subjects with PBC, treatment with OCA has been shown to cause a dose-dependent exacerbation of this common symptom and similar results can be expected in subjects with PSC. Pruritus has also been observed in clinical trials with OCA in other indications and in healthy volunteers, but at a lower frequency and at higher doses than that observed in subjects with chronic cholestasis. Investigator guidance for pruritus management strategies are outlined in [Section 11.1.3.1](#) of the protocol.

Other potential risks include liver toxicity, especially at higher doses of OCA, which is consistent with nonclinical findings and the chemical characteristics of OCA as a bile acid and detergent. An increase in liver function tests and hepatobiliary AEs, including jaundice, ascites and acute cholecystitis were observed in subjects with PBC and NASH who were treated at doses that are several fold higher (primarily 20 mg to 50 mg daily) than those studied in this

protocol (1.5 mg, 3 mg, 5 mg, and 10 mg) doses. This is an important potential risk in subjects with PSC, where there is the possibility of dominant strictures of intra- and extra-hepatic bile ducts that could restrict bile flow. In order to monitor bile duct patency, the trial protocol requires that sites perform an ultrasound at Screening, at the end of the DB phase, and annually in the LTSE. Consistent with this potential risk, the present trial excludes subjects who have had, or who are suspected of having, a recent dominant stricture ([Section 7.3](#)). In addition, the trial calls for mandatory discontinuation of investigational product in those subjects whose liver chemistry (AST, ALT and or bilirubin) display clinically significant increases following the initiation of therapy ([Section 7.4.1](#)). The doses used in the present trial (1.5 mg to 10 mg) are amongst the lowest doses of OCA tested to date in a clinical setting.

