### **Clinical Laboratory Values**

Development of the following clinical laboratory values, without explanation, during the course of the DB and LTSE phases of the trial mandates investigational product discontinuation:

- AST and/or ALT >3x ULN **AND** 2x the Baseline value **OR**
- Two consecutive measurements of total bilirubin >ULN **AND** >2x the Baseline value in the absence of evidence of new biliary obstruction.

The term “Baseline” within this protocol, unless otherwise specified, is intended to mean, “pretrial” or “pretreatment” (of investigational product). It refers to values obtained during the Screening, retests, or Day 0 visits, prior to the subject’s first dose of investigational product.

If a subject is required to discontinue investigational product due to an increase in AST, ALT, or bilirubin, the subject must be followed at appropriate intervals until these parameters have returned to within the normal range or pretrial values, and/or are stable or there is are stable, or there is no ongoing clinical concern.

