6. GENERAL ANALYSIS CONSIDERATIONS

6.1. Data Reporting

The statistical analyses will be reported using summary tables, figures, and data listings.

Laboratory units will be summarized and presented both in conventional units (CV) and in the international system of units (SI).

Individual subject data obtained from the electronic case report forms (eCRFs), external laboratory data, and any derived data (such as change from Baseline and percent change from Baseline) will be presented in data listings by subject. Data from all assessments, whether scheduled or unscheduled, will be listed by subject and visit. Unscheduled visits and visits occurring more than one day outside protocol defined window will not be included in the table summaries, excluding transient elastography measurements.

The analyses described in this plan are considered a priori, in that they have been defined prior to database lock of the DB phase. Post hoc analyses will be labeled as such on the outputs and identified in the CSR.

All analyses and tabulations will be performed using SAS® Version 9.2 or higher. PK parameters will be estimated using Phoenix® WinNonlin® Version 6.3. The following processes will be employed to validate statistical outputs: derived datasets (both tabulation datasets and analysis datasets), summary tables, and data listings will be verified through independent programming; graphical displays will be compared against supporting summary tables; and all outputs will undergo a senior-level statistical review. The process includes confirmation that statistically valid methods have been implemented and that all data manipulations and calculations are appropriate and accurate. Checks will be made to ensure accuracy, adherence to this SAP, consistency within tables, and agreement between tables and their corresponding data listings. Upon completion of validation/verification and quality review procedures, all documentation will be collected and filed in the study master file by the project statistician or designee.

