8.3. Demographic and Baseline Characteristics

Demographic variables will include the following:

- Age at informed consent
- Age at informed consent categorized as <65 years and ≥ 65 years
- Sex
- Race/Ethnicity

Other Baseline characteristics will include the following:

- Weight (kg)
- Height (cm)
- BMI (kg/m^2)
- BMI categorized as $<30 \text{ kg}/\text{m}^2$ and $\geq 30 \text{ kg}/\text{m}^2$
- Hepatic ultrasound to assess bile duct patency performed (Yes/No)
- Key liver function test results as a continuous variable and categorized as follows by the ULN and the LLN unless otherwise specified:
 - ALP: $\leq 3 \times \text{ULN}$, $>3 \times \text{ULN}$; and, $\leq \text{median baseline ALP}$, $> \text{median baseline ALP}$

- Total Bilirubin: \leq ULN, $>$ ULN, $>$ ULN - \leq 1.5xULN, $>$ 1.5xULN - \leq 2xULN, $>$ 2xULN - \leq 2.5xULN
- International normalized ratio (INR): \leq 1.3, $>$ 1.3 stratified by subjects on/not on anticoagulants at the time of randomization

Arithmetic summary statistics as described in [Section 6.2.1](#) will be presented for age, weight, height, BMI, and key liver function test results. Frequency counts and percentages will be presented for age groups, sex, race/ethnicity, BMI category, key liver function categories, and hepatic ultrasound.

Race and ethnicity will be summarized as follows:

- Race
 - American Indian or Alaska Native
 - Asian
 - Black or African American
 - Native Hawaiian or Other Pacific Islander
 - White
- Ethnicity
 - Hispanic or Latino
 - Not Hispanic or Latino
 - Not reported
 - Unknown

Demographic and Baseline characteristics will be summarized for the ITT, Safety, PK, W12C, and W24C populations. All demographic and Baseline characteristics will be presented in data listings. The subgroup tables will be generated for IBD, UC, and CD regardless of the total number of patients in each group. For the remaining subgroups, the tables will be generated as long as each subgroup contains at least 10% of the subjects in the overall population.

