10.3. Adverse Events of Special Interest

Adverse events of special interest (AESI) are pruritus, and dyslipidaemia. For each of these AESI, subject incidence of TEAEs and the total number of entries by MedDRA system organ class and preferred term will be presented. In addition, for each AESI, the time to first onset and time to most severe event will be summarized using descriptive statistics.

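### The laboratory safety tables are insensitive to liver injury: re-test and unscheduled results stay out of the summaries, shifts are only low-normal-high, and no table counts subjects who cross the protocol 7.4.1 thresholds

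*SAP*

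**What the plan says.** Protocol 4.5 tells investigators: "Other potential risks include liver toxicity, especially at higher doses of OCA". It then adds: "This is an important potential risk in subjects with PSC". Protocol 7.4.1 turns this into laboratory rules: "Development of the following clinical laboratory values, without explanation, during the course of the DB and LTSE phases of the trial mandates investigational product discontinuation". The rules cover AST or ALT above 3x ULN together with 2x Baseline, and two consecutive total bilirubin values above ULN and above 2x Baseline. Protocol 5.1 and SAP 2 make safety a primary objective.

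The SAP's laboratory tables work as follows.

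- SAP 10.4: "Re-tests or unscheduled visit results after first dose of investigational product in the DB phase will not be summarized". These results go to listings.
- SAP 6.1, as a general rule: "Unscheduled visits and visits occurring more than one day outside protocol defined window will not be included in the table summaries". Transient elastography is the only exception.
- SAP 10.4 plans "shift tables (ie, low-normal-high at Baseline versus low-normal-high at DB post-Baseline Visit in a 3-by-3 contingency table) from Baseline to worst value", and the same to last value and to each scheduled visit. Neither worst value nor last value is defined.
- SAP Appendix A lists the serum chemistry shift by treatment and visit. It has no safety table of post-dose elevations by multiples of ULN or Baseline, and none of subjects meeting 7.4.1.

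**The concern.** The protocol judges liver injury by how far a value has risen relative to ULN and to the subject's own Baseline. The SAP's shift tables record only which side of the normal range a value lies on. In a population selected for cholestasis, many subjects are already on the high side.

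The results that best describe a hepatic event may also be re-tests, unscheduled safety samples (Protocol 8.6.23) or samples taken at early withdrawal. Under SAP 6.1 and 10.4 these may reach only the listings. At stake is whether a reader of the laboratory safety tables could see that subjects in one arm had crossed the protocol's own stopping thresholds.

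**Working it through.** The plan gives no figure on this point, so there is nothing to reproduce. The check sets the rules side by side and classifies subjects at the 7.4.1 thresholds.

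**Inputs.** Screening ALP at least 2x ULN (Protocol 7.2). Baseline is the average of the pre-dose values (SAP 6.3.1). Thresholds from Protocol 7.4.1. Bilirubin cap of 25% (Protocol 7.1). Chemistry at Weeks 2, 6, 12, 14, 18 and 24 (Protocol Table 1). About 25 subjects per arm.

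**ALP.** With one Screening value of at least 2 and a Day 0 value d (both in multiples of ULN), Baseline is at least (2 + d)/2, which exceeds 1 for any positive d. If a second Screening sample was needed to bring the Screening mean to 2, Baseline is at least (4 + d)/3, again above 1. Every subject therefore starts in the high category, and no upward ALP shift can be tabulated.

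**ALT and AST.** For Baseline b, the value must exceed max(3, 2b).

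| Baseline (x ULN) | Threshold (x ULN) | Shift cell |
|---|---|---|
| 0.6 | 3 | normal to high |
| 1.0 | 3 | normal to high |
| 1.2 | 3 | high to high |
| 1.5 | 3 | high to high |
| 2.0 | 4 | high to high |
| 3.0 | 6 | high to high |

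**Total bilirubin.** Two consecutive values must exceed max(1, 2b).

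| Baseline (x ULN) | Threshold (x ULN) | Shift cell |
|---|---|---|
| 0.6 | 1.2 | normal to high |
| 1.0 | 2.0 | normal to high |
| 1.2 | 2.4 | high to high |
| 1.6 | 3.2 | high to high |
| 2.4 | 4.8 | high to high |

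The cap allows 0.25 × 75 = 18.75, so at most 18 subjects above 1.5x ULN at Screening. A rise in these subjects would not show if their averaged Baseline is still above ULN. With Screening just over 1.5, that fails only if Day 0 is about 0.5x ULN or lower, since (1.5 + 0.5)/2 = 1.

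**Which results count.** Intervals between scheduled chemistry samples, from Day 0, are 2, 4, 6, 2, 4 and 6 weeks. The two 6-week intervals cover 12 of 24 weeks. A peak found at an unscheduled visit in between is not summarised. The second bilirubin value needed for 7.4.1 may be a scheduled sample or a re-test; a re-test is only listed. The SAP gives no rule for assigning an early end-of-treatment sample to a visit, so SAP 6.1 could exclude that too.

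**Size.** The documents give no hepatic event rate. For assumed rates of 2%, 5% and 10%, expected events per arm are 25p = 0.5, 1.25 and 2.5. The chance of at least one, 1 − (1 − p)^25, is 40%, 72% and 93%. With so few events, one omitted value can change what a table shows.

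**The case against.** The strongest reply is that hepatic harm has several other routes into the report, and this stands.

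- Subjects who meet 7.4.1 must stop product. They would be counted among permanent discontinuations (SAP 10.1.1), under reason for discontinuation if they leave the double-blind phase (SAP 8.1), and among adverse events leading to withdrawal if the finding is recorded as an adverse event (SAP 10.2).
- Serum chemistry is summarised by arm and visit with maxima (SAP 6.2.1 and 10.4). An ALT of 12x ULN at a summarised scheduled visit would appear as that arm's maximum.
- ALT, AST and bilirubin are analysed by ANCOVA and MMRM (SAP 9.2, Appendix A), listings are complete and flagged, and the DSMC reviews laboratory data and SAEs.

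A reader might infer that liver toxicity could pass unseen through the whole report. Given these outputs, the documents do not support that. What the outputs lack is a count. Means dilute one or two cases among 25, a maximum does not show whether a subject met 7.4.1, and adverse event tables depend on how investigators report.

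Three other strong readings also fail. Not all subjects start high on every liver test: this is certain only for ALP, which is not a 7.4.1 analyte. Protocol 4.1 says ALT and GGT are raised typically but not always, and that bilirubin is often normal early in the disease. The SAP does not say outright that worst value excludes unscheduled results; that is inferred from 6.1 and 10.4. And "Adverse events of special interest (AESI) are pruritus, and dyslipidaemia" is a sponsor's choice, not an error. No rule in either document requires a hepatic category, although Protocol 4.5 would justify one.

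**Conclusion.** The point holds as a weakness of the laboratory safety tables, not as a hidden safety signal. For ALP, upward shifts are impossible by design. For ALT, AST and bilirubin, a subject above ULN at Baseline can meet a mandatory stopping threshold and still be tabulated as unchanged. How many subjects this affects is not given; for bilirubin, up to 18 may enter above 1.5x ULN. No planned safety table would recover the count. The SAP does count subjects by ULN and Baseline multiples elsewhere, for Baseline categories (8.3) and ALP response (5.2.1), but not for post-dose elevations.

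The conclusion rests on reading worst and last value under the exclusions in SAP 6.1 and 10.4. If the sponsor intends them to include all results, one sentence settles that part, and the limits of the shift format and the missing counts remain.

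A reader might also infer that the Week 24 ultrasound finding is being withheld. The SAP's only ultrasound variable is "Hepatic ultrasound to assess bile duct patency performed (Yes/No"), and the documents do not show that a codable patency result is captured.

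**What to change.** In SAP 10.4:

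1. State that worst and last values use every post-dose double-blind result: scheduled, out-of-window, end-of-treatment, re-test and unscheduled. Keep scheduled visits for by-visit means, and make this an explicit exception to SAP 6.1.
2. For ALT, AST, ALP and total bilirubin, add by-arm tables of the worst value in multiples of ULN and of Baseline.
3. Count, by arm, subjects meeting each 7.4.1 laboratory criterion as written. Say which Baseline is used, since SAP 6.3.1 averages the pre-dose values and Protocol 8.6.3 allows the analysis definition to differ. The qualifiers in 7.4.1 (no other explanation, no new biliary obstruction) cannot be derived from laboratory values and should be noted beside the count.

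The cost is SAP wording and a few tables from laboratory data already collected. No protocol amendment is needed, and no stopping rule changes. The small downside is that worst-value tables may look less favourable for subjects tested more often, so the number of tests per subject could be shown alongside.

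A prespecified hepatobiliary adverse event grouping is an optional addition. So is a table of ultrasound patency at Screening against Week 24, if that result is captured.

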10.5. Vital Signs

Vital signs (oral temperature, sitting heart rate, respiratory rate, and sitting blood pressure [systolic and diastolic]) will be summarized using arithmetic summary statistics as described in [Section 6.2.1](#) at Baseline and at each DB post-Baseline visit. Change from Baseline will also be summarized in the same manner. Re-tests or unscheduled visit results prior to the administration time of the first dose in the DB phase will be included in the calculation of Baseline. Re-tests or unscheduled visit results after the first dose of investigational product administration will not be summarized but will be included in the data listings.

10.6. ECGs (ECGs)

Overall interpretation results for ECGs and the Investigator interpretation results are collected as normal, abnormal-not clinically significant, and abnormal-clinically significant. Subjects whose interpretation shifts from normal at Baseline to abnormal at any DB post-Baseline visit will be summarized by treatment group and visit. In addition, these will be listed separately including description of the abnormality and any associated comments.

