### **Safety Analyses**

The incidence of treatment emergent adverse events (TEAEs) and serious adverse events (SAEs) will be tabulated by system organ class and preferred term for each treatment group, and similarly by severity and relationship to treatment.

Laboratory parameters and vital signs will be summarized by treatment group using descriptive statistics at Baseline and at each scheduled post-Baseline visit. The change from Baseline will also be summarized. Electrocardiograms (ECGs) will be summarized by treatment group using frequency at each visit. The shift from baseline will also be summarized. Baseline is defined as the mean of all available evaluations prior to treatment (except for lipoprotein assessments where Baseline will be Day 0).

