### **11.2.4. Electrocardiogram**

Standard 12-lead ECGs will be collected. The Investigator or designee will review the 12-lead ECG and findings will be recorded in the CRF as normal, abnormal but not clinically significant, or abnormal and clinically significant. Any clinically significant abnormalities on ECGs recorded after Screening will also be documented as AEs and entered on the AE page of the CRF.

Investigative sites must retain a copy of all 12-lead ECGs evaluated by the Investigator or designee. These ECGs must be clearly labeled with the Subject ID number, date and time.

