### **12.5.3. Additional Safety Analysis**

Additional safety assessments include vital signs and ECGs. Vital signs will be summarized by treatment group using descriptive statistics at Baseline and at each scheduled post-Baseline visit. The change from Baseline will also be summarized. ECGs will be summarized by treatment group using frequency at each visit. The shift from baseline will also be summarized. Baseline is defined as the mean of all available evaluations prior to treatment.

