| 14.3.4.4 | Safety | Summary of Nuclear Magnetic Resonance Lipoprotein Panel by Treatment and Visit |
| 14.3.4.5 | Safety | NMR Lipoprotein Shift Analysis by Treatment and Visit |
| 14.3.4.6 | Safety | Summary of Vital Signs by Treatment and Visit |
| 14.3.4.7 | Safety | Electrocardiogram Shift from Baseline by Treatment |

List of Figures

| Figure Number | Population | Figure Title |
|----------------|------------|---|
| 14.2 | | Efficacy Data |
| 14.2.1.1 | PK | Individual Plasma Concentration of OCA (Unconjugated) Over Time |
| 14.2.1.2 | PK | Individual Plasma Concentration of Glyco-OCA Over Time |
| 14.2.1.3 | PK | Individual Plasma Concentration of Tauro-OCA Over Time |
| 14.2.1.4 | PK | Individual Plasma Concentration of Total OCA Over Time |
| 14.2.2.1 | PK | Mean (SD) Plasma Concentration of OCA (Unconjugated) Over Time |
| 14.2.2.2 | PK | Mean (SD) Plasma Concentration of Total Glyco-OCA Over Time |
| 14.2.2.3 | PK | Mean (SD) Plasma Concentration of Total Tauro-OCA Over Time |
| 14.2.2.4 | PK | Mean (SD) Plasma Concentration of Total OCA Over Time |
| 14.2.3.1.1.1 | PK | Scatter Plot of Week 12 ALP versus Total OCA AUC ₀₋₆ |
| 14.2.3.1.1.2 | PK | Scatter Plot of Week 24 ALP versus Total OCA AUC ₀₋₆ |
| 14.2.3.1.2.1 | PK | Scatter Plot of Week 12 Change from Baseline in ALP versus Total OCA AUC ₀₋₆ |
| 14.2.3.1.2.2 | PK | Scatter Plot of Week 24 Change from Baseline in ALP versus Total OCA AUC ₀₋₆ |
| 14.2.3.2.1.1 | PK | Scatter Plot of Week 12 Total Bile Acids versus Total OCA AUC ₀₋₆ |
| 14.2.3.2.1.2 | PK | Scatter Plot of Week 24 Total Bile Acids versus Total OCA AUC ₀₋₆ |
| 14.2.3.2.2.1 | PK | Scatter Plot of Week 12 Change from Baseline in Total Bile Acids versus Total OCA AUC ₀₋₆ |
| 14.2.3.2.2.2 | PK | Scatter Plot of Week 24 Change from Baseline in Total Bile Acids versus Total OCA AUC ₀₋₆ |
| 14.2.3.3.1.1.1 | PK | Scatter Plot of Week 12 UCDA (conjugated) versus Total OCA AUC ₀₋₆ |
| 14.2.3.3.1.1.2 | PK | Scatter Plot of Week 12 UCDA (unconjugated) versus Total OCA AUC ₀₋₆ |
| 14.2.3.3.1.2.1 | PK | Scatter Plot of Week 24 UCDA (conjugated) versus Total OCA AUC ₀₋₆ |
| 14.2.3.3.1.2.2 | PK | Scatter Plot of Week 24 UCDA (unconjugated) versus Total OCA AUC ₀₋₆ |
| 14.2.3.3.2.1.1 | PK | Scatter Plot of Week 12 Change from Baseline in UCDA (conjugated) versus Total OCA AUC ₀₋₆ |
| 14.2.3.3.2.1.2 | PK | Scatter Plot of Week 12 Change from Baseline in UCDA (unconjugated) versus Total OCA AUC ₀₋₆ |

| | | |
|----------------|----|---|

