| 16.2.5.5.1 | Plasma Concentration Collection Information |
| 16.2.5.5.2 | Plasma Concentration Data for OCA, Glyco-OCA, Tauro-OCA, and Total OCA |
| 16.2.5.5.3 | Plasma PK Parameters for OCA, Glyco-OCA, Tauro-OCA, and Total OCA |
| 16.2.5.6.1 | Bile Acids and Bile Acid Subcomponents |
| 16.2.5.6.2 | Total Bile Acids and Total Endogenous Bile Acids |
| 16.2.6 | Individual efficacy response data |
| 16.2.6.1 | Alkaline Phosphatase |
| 16.2.6.2 | Hepatic Biochemistry and Indices of Function |
| 16.2.6.3 | Markers of Hepatic and GI Inflammation and Disease |
| 16.2.6.4 | Transient Elastography |
| 16.2.6.5 | Enhanced Liver Fibrosis Score and Components |
| 16.2.6.6 | Farnesoid X Receptor Activity |
| 16.2.6.7.1 | Pruritus Visual Analogue Scale Scores |
| 16.2.6.7.2 | Pruritus 5-D Itch Scores |

| | |
|---------------|--|
| 16.2.6.8 | Partial Mayo Score |
| 16.2.6.9 | Chron's Disease Activity Index Score |
| 16.2.6.10 | Transient Elastography |
| 16.2.7 | Adverse events listings |
| 16.2.7.1 | Adverse Events |
| 16.2.7.2 | Serious Adverse Events |
| 16.2.7.3 | Severe Adverse Events |
| 16.2.7.4 | Adverse Events Leading to Investigational Product Withdrawal or Study Discontinuation |
| 16.2.7.5 | Adverse Events Related to Investigational Product |
| 16.2.7.6 | Adverse Events Leading to Investigational Product Withdrawal |
| 16.2.7.7 | Adverse Events Leading to Investigational Study Discontinuation |
| 16.2.7.8 | Adverse Events Leading to Death |
| 16.2.8 | Listing of individual laboratory measurements by subject, when required by regulatory authorities |
| 16.2.8.1 | Laboratory Sample Collection |
| 16.2.8.2 | Hematology and Coagulation |
| 16.2.8.3.1 | Serum Chemistry – SI Units |
| 16.2.8.3.2 | Serum Chemistry – CV Units |
| 16.2.8.4 | Urinalysis |
| 16.2.8.5 | Apolipoprotein and NMR Lipoprotein |
| 16.2.8.6.1 | Laboratory Reference/Normal Ranges – SI Units |
| 16.2.8.6.2 | Laboratory Reference/Normal Ranges – CV Units |
| 16.2.9 | Additional Safety Listings |
| 16.2.9.1 | Vital Signs |
| 16.2.9.2 | 12-lead Electrocardiograms (ECGs) |
| 16.2.9.3 | Pregnancy Test Results |
| 16.2.9.4 | Historical and On-Study Procedures |
| 16.2.9.5 | Subject Visit Information |
| 16.2.9.6 | Subject Reconsent |
| 16.2.9.7 | Comments |

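### The SAP's ECG summary covers only subjects who go from normal to abnormal, and it omits the by-visit frequencies the protocol specifies without declaring the change

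*SAP*

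**What the plan says.** Protocol 11.2.4 has each ECG "recorded in the CRF as normal, abnormal but not clinically significant, or abnormal and clinically significant". SAP 10.6 uses the same three grades: "collected as normal, abnormal-not clinically significant, and abnormal-clinically significant".

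For analysis, protocol 12.5.3 states: "ECGs will be summarized by treatment group using frequency at each visit. The shift from baseline will also be summarized". The synopsis gives the same instruction: "Electrocardiograms (ECGs) will be summarized by treatment group using frequency at each visit". Neither place limits the shift to a particular Baseline grade.

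SAP 10.6 plans something narrower: "Subjects whose interpretation shifts from normal at Baseline to abnormal at any DB post-Baseline visit will be summarized by treatment group and visit". It then adds: "In addition, these will be listed separately including description of the abnormality and any associated comments". The word *these* points back to the normal-to-abnormal subjects, so the separate listing carries the same restriction.

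SAP Appendix A has a single ECG table, 14.3.4.7, titled "Electrocardiogram Shift from Baseline by Treatment", and a general ECG data listing, 16.2.9.2. SAP Section 11, which is reserved for changes to protocol-specified analyses, mentions only gut microbiome and genetic samples.

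**The concern.** Safety is one of the two primary objectives (protocol 5.1, SAP Section 2), and the ECG is one of the safety assessments that the protocol says will be summarized. A three-grade scale lets a reader see whether an existing abnormality became clinically significant on treatment. A summary that starts only from normal ECGs cannot show that.

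The missing frequencies add to this. Without category counts at Baseline and at the end of the phase, a reader of the tables cannot tell how many subjects per arm were already abnormal at entry, and so cannot tell how many lay outside the summary. SAP 10.6 also names no denominator.

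What is at stake is the completeness of one safety table and its agreement with the protocol. The efficacy analysis, the error rates and the data collected are not affected.

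**Working it through.** The plan states no figure here and no power or error-rate calculation applies. The check sets the texts side by side and enumerates the shift cells.

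**Step 1: shift cells.** Three Baseline grades by three post-Baseline grades give 3 × 3 = 9 cells.

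| Baseline | Post-Baseline normal | Post-Baseline NCS | Post-Baseline CS |
|---|---|---|---|
| Normal | unchanged | worse, in the SAP summary | worse, in the SAP summary |
| NCS | better | unchanged | worse, **not** in the SAP summary |
| CS | better | better | unchanged |

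Three cells are unchanged, three improve and three worsen. The SAP 10.6 rule reaches 2 of the 3 worsening cells. The one it misses is NCS to CS.

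**Step 2: protocol against SAP.**

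| Item | Protocol 12.5.3 and synopsis | SAP 10.6 and Appendix A |
|---|---|---|
| Frequency at each visit | planned | absent |
| Shift from Baseline | planned, no limit on Baseline grade | limited to normal at Baseline in 10.6; the title of Table 14.3.4.7 states no limit |
| Change declared in SAP Section 11 | not applicable | no |

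**Step 3: how many visits are involved.** Table 1 of the protocol schedules the double-blind ECG at Screening and at Week 24/EOT only. Frequency at each visit therefore means two time points, and the shift is a single paired comparison per subject. The missing frequencies amount to 2 time points × 3 grades = 6 counts per arm.

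**Step 4: where else an NCS-to-CS change would appear.** Protocol 11.2.4 requires a clinically significant abnormality on an ECG after Screening to be recorded as an adverse event. If it is new or worse after the first dose, it meets the SAP 10.2 definition of treatment-emergent and enters the tables by treatment group on the Safety population. SAP 6.1 also lists all assessments by subject and visit, and Listing 16.2.9.2 covers ECGs. The change is thus missing from the ECG summary and its separate listing, not from the report.

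**Step 5: comparison within the SAP.** For hematology, coagulation and serum chemistry, SAP 10.4 specifies a full 3-by-3 shift table (low, normal, high). The same layout fits a three-grade ECG result, and the SAP gives no reason for treating ECGs differently.

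**What cannot be sized.** The documents do not say how many subjects are expected to have an NCS ECG at Baseline. With about 25 subjects per arm, each such subject is 1/25 = 4% of the arm. No estimate of the number is offered.

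**The case against.** The best defence is that little is lost. A subject who reaches CS is captured as an adverse event, is tabulated by arm with a denominator if treatment-emergent, and appears in the data listing. With one scheduled post-Baseline ECG, the by-visit requirement is nearly empty. The SAP's adverse events of special interest are pruritus and dyslipidaemia (SAP 10.3), and protocol 4.5 names no cardiac risk. The protocol asks for a shift from Baseline without prescribing a 3x3 layout, and the title of Table 14.3.4.7 would accommodate a full shift table.

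Most of this stands, and it sets the size of the point. Four stronger readings that a reader might infer are not supported:

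- *NCS-to-CS worsening would never be counted.* The adverse-event route and Listing 16.2.9.2 should both show it.
- *Subjects abnormal at Baseline are a second, separate omission.* On this scale such a subject can worsen only from NCS to CS, so it is the same cell.
- *The two abnormal grades will be merged.* SAP 10.6 names both grades and then says abnormal. It does not say the table will collapse them, and the table shell is not in the documents.
- *A series of by-visit tables has been dropped.* There are only two scheduled time points.

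What the defence does not remove is the mismatch in the text. The governing sentence in SAP 10.6 is narrower than the protocol, the frequencies are planned nowhere in the SAP, and Section 11 is silent. Adverse-event tables arranged by system organ class and preferred term do not show Baseline ECG grade or a paired shift. The 3x3 table is one way to meet the protocol's general wording and is not itself a protocol requirement.

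**Conclusion.** The point holds as a minor misalignment between protocol and SAP. Followed as written, SAP 10.6 leaves one of three worsening transitions, NCS to CS, out of the ECG summary and its separate listing. The frequencies that the protocol specifies are missing from SAP 10.6 and Appendix A, with no declaration in Section 11.

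The practical effect is small, for the reasons in Steps 3 and 4 of the working. This conclusion assumes that Table 14.3.4.7 would be programmed from the text of SAP 10.6 rather than from its broader title, and that sites record CS findings as adverse events as protocol 11.2.4 requires. The documents give no basis for saying that ECG harm would go unseen in the trial.

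**What to change.** In SAP 10.6, replace the sentence on normal-to-abnormal shifts with the following:

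- A 3x3 shift table (normal, NCS, CS) by treatment group, from Baseline to the double-blind post-Baseline ECG at Week 24/EOT. The denominator is subjects with both ECGs.
- Counts and percentages in each category by treatment group at Baseline and at Week 24/EOT.
- The separate listing kept, and extended to any subject who worsens by one grade or more.

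Align Table 14.3.4.7 with this text. The present wording refers to any double-blind post-Baseline visit, whereas SAP 6.1 keeps unscheduled and out-of-window visits out of the tables. The new text should therefore say which ECG is used for subjects who stop early, and that other ECGs appear in the listing only. If the narrower summary is intended, state and justify it in SAP Section 11 instead.

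The cost is one table shell. No new data are needed.
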